8.6 Data Management

Data will be collected in ad hoc Excel file. To guarantee data protection, patients will be indicated with a unique pseudonymized code. Each process to promote data quality will be guaranteed. Data insertion in the database will be performed in a correct and accurate way according to the source documentation. To ensure adequate control over the quality of the study, the investigator will allow, if required from the regulatory authorities, direct access to all relevant documentation and devote part of his time to discuss the study results.

All the information collected in our database will be treated in accordance with the provisions of the European Privacy Regulation (General Data Protection Regulation UE 2016/679) and Italian legislation.

Dipartimento Area dei Servizi
SC Medicina Trasfusionale

Direttore: [name]

Tel. Segreteria Direzione: [name]

E-mail: [contact]; [contact]

8.7 Statistical Analysis

For descriptive analyses, quantitative variables will be expressed as mean and standard deviation or as median, interquartile range (IQR) and minimum-maximum range, while categorical variables will be expressed as absolute and relative frequencies.

Aiming to evaluate the impact of clinical and biochemical variables on CD34+ CE, we will examine the association between CD34+ CE and age, sex, type of donor (patients vs healthy donors), hematocrit, hemoglobin level, WBC counts, platelets count.

Analysis will be performed by fitting data in generalized linear models for continuous variables and logistic regression for binary variables. In order to avoid overfitting, the selection of variables to be included in multivariable models will be performed by Backward stepwise regression. All models will be adjusted for significant clinical confounders.

Statistical analysis will be performed using the JMP Pro 16.0 Statistical Analysis Software (SAS Institute, Cary, NC). P values <0.05 (two tailed) were considered statistically significant.

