The CE values are affected by different factors among which blood sample's physical properties. Such factors have been widely studied in MNC protocol⁷, but less studies concern the cMNC protocol⁸. In 147 consecutive apheresis procedures performed both on patients and healthy donors with Spectra Optia (Terumo BCT) with cMNC system, Kondo et colleagues found a moderate positive correlation between CD34+ CE and hematocrit (Ht) and only a very weak correlation with white blood cells (WBC) and platelet counts. We would like to confirm these data in a setting of subjects with a predominance of patients over healthy donors, thus evaluating the influence of clinical and biochemical factors on CE for autologous and allogenic hematopoietic stem cell production. Finally we would like to assess a possible pre-LP Ht threshold associated with a sufficient (> 60%) CD34+ CE⁹.

Dipartimento Area dei Servizi
SC Medicina Trasfusionale

Direttore: [name]

Tel. Segreteria Direzione: [name]

E-mail: [contact]; [contact]

7. Objectives of the study

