8.1.1 Primary Endpoint

Impact, measured by statistical correlation, of clinical (age, sex, type of donor, diagnosis, recent RBC transfusion) and biochemical (pre-LP values of Ht, Hb, WBC and PLT) variables on CD34+ CE.

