8.5 Sample Size

Total study population: 113 subjects of which 74 hematological/non hematological patients and 39 stem cell donors.

The number of subjects evaluated is determined by the clinical activity of the Apheresis Unit (SC Medicina Trasfusionale) and has been considered adequate considering the number of subjects included in other similar study present in the literature^{7,8}. Due to descriptive nature of the analysis planned, no pre-analysis sample size was determined.

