8.7.1 Primary Endpoint: analysis

Influence of biological variables on CD34+ CE will be evaluated using a stepwise backward regression analysis; correlation intensity will be assessed using generalized linear model of regression and strength of correlation will be determined by estimate and standard error value.

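### Haematocrit and haemoglobin both enter the backward selection and nothing protects haematocrit, so the multivariable result can name Hb in place of the variable the study sets out to confirm

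*Combined protocol and SAP*

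**What the plan says.** The primary endpoint (8.1.1) relates CE to clinical variables and to "pre-LP values of Ht, Hb, WBC and PLT". The first secondary endpoint (8.1.2) uses the same four blood-count variables for adequate CE. Section 8.7 names the variables to be examined as "age, sex, type of donor (patients vs healthy donors), hematocrit, hemoglobin level, WBC counts, platelets count".

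On model building, 8.7 states that "the selection of variables to be included in multivariable models will be performed by Backward stepwise regression", and 8.7.1 applies this to the primary endpoint: "Influence of biological variables on CD34+ CE will be evaluated using a stepwise backward regression analysis". The only threshold given is in 8.7: "P values <0.05 (two tailed) were considered statistically significant". All models are also to be adjusted for significant clinical confounders, but these are not named and Ht is not said to be one of them. No section forces Ht into a model, chooses between Ht and Hb in advance, or sets a collinearity check.

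The specific hypothesis is stated in Ht. The background says that a published study of the same collection system "found a moderate positive correlation between CD34+ CE and hematocrit (Ht"), and adds an interest in a pre-procedure Ht threshold. Section 7.2 makes confirming the Ht–CE correlation a secondary objective. Section 8.1.2 gives it its own endpoint, which does not mention Hb.

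**The concern.** Ht and Hb are two readings from one blood count and can be expected to correlate strongly. When both are offered to backward elimination, one usually removes the other, and which one survives depends partly on sampling noise. Section 8.7.1 judges strength by the estimate and standard error from the regression, so a variable that has been eliminated has no result to report.

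The final model could therefore show Hb as significant with Ht absent, even if Ht is what drives CE. A reader could take that as failure to confirm the published Ht finding, when the two variables are merely standing in for each other.

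**Working it through.** **Inputs from the documents.** N = 113, from 8.5: "Total study population: 113 subjects of which 74 hematological/non hematological patients and 39 stem cell donors" (74 + 39 = 113, which agrees). Section 8.9 restricts the analysis to each patient's first procedure. There are seven candidates (8.7), with backward selection and two-sided 0.05. The plan gives no collinearity, power or sample size figure to reproduce.

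**Assumptions.** Ht–Hb correlation r between 0.90 and 0.99. Ht–CE correlation between 0.24 and 0.5, because the plan says only that the published value was moderate. The 0.05 level is also taken as the threshold for staying in the model. The correlations among the other covariates are assumed too (for example donor–Ht 0.5).

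**Step 1: inflation in the starting model.** For the pair alone, VIF = 1/(1 − r²), and the SE is multiplied by √VIF.
- r = 0.90: 1/0.19 = 5.3; SE × 2.3
- r = 0.95: 1/0.0975 = 10.3; SE × 3.2
- r = 0.97: 1/0.0591 = 16.9; SE × 4.1
- r = 0.99: 1/0.0199 = 50.3; SE × 7.1

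In the simulated seven-variable model the Ht SE was 2.1 to 6.2 times its value without Hb.

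**Step 2: what selection keeps when Ht is the only true driver.** Backward elimination, 1,500 datasets per row. The Monte Carlo SE near 30% is √(0.3 × 0.7/1500) = 1.2 points.

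| Ht–CE | r | Ht only | Hb only | Both | Neither | Ht dropped if Hb is not offered |
|---|---|---|---|---|---|---|
| 0.3 | 0.90 | 66.6% | 20.1% | 2.1% | 11.2% | 12.9% |
| 0.3 | 0.95 | 57.3% | 28.4% | 2.4% | 11.9% | 14.2% |
| 0.3 | 0.97 | 55.5% | 29.9% | 3.1% | 11.5% | 13.3% |
| 0.3 | 0.99 | 51.5% | 34.5% | 2.7% | 11.3% | 12.6% |
| 0.4 | 0.90 | 81.0% | 16.1% | 2.0% | 0.9% | 1.3% |
| 0.4 | 0.95 | 71.7% | 24.2% | 2.9% | 1.1% | 1.3% |
| 0.4 | 0.97 | 65.7% | 30.3% | 2.3% | 1.7% | 1.9% |
| 0.4 | 0.99 | 58.6% | 37.3% | 3.1% | 1.1% | 1.3% |
| 0.5 | 0.90 | 87.2% | 9.6% | 3.2% | 0.0% | 0.0% |
| 0.5 | 0.99 | 63.9% | 33.2% | 2.9% | 0.1% | 0.1% |

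A separate run over r = 0.90 to 0.98 and Ht–CE 0.24 to 0.4 gave Hb in place of Ht in 18% to 36% of datasets and both kept in 2% to 4%. Neither was kept in 0.4% to 26%; with Hb not offered, Ht was dropped in 0.7% to 31%.

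**Step 3: if Ht and Hb carry the same signal.** Over Ht–CE 0.3 to 0.5, Hb alone was kept in 43% to 52% of datasets and Ht alone in 43% to 51%. At 0.4 and r = 0.97 the split was 50% to 48%.

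**Step 4: the simple association.** Power ≈ Φ(atanh(ρ)·√(N − 3) − 1.96). With N = 113 and ρ = 0.3: 0.3095 × 10.488 − 1.96 = 1.29, which gives 90%. With ρ = 0.4: 0.4236 × 10.488 − 1.96 = 2.48, which gives 99%. In the 74 patients alone the values are 74% and 95%. None of these depends on Hb.

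**The case against.** Four points on the other side carry weight.

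- **Selection is not a coin toss.** A reader might infer that it picks between the two almost at random. If Ht is the true driver, Ht is favoured, from about 1.5:1 (51.5% to 34.5%) to 9:1 (87.2% to 9.6%). An even split arises only if both carry the same signal.
- **The effect is not lost.** A reader might infer that including Hb makes a real red-cell effect easier to miss. Step 2 shows otherwise: neither is kept about as often as, or slightly less often than, Ht is dropped when Hb is not offered.
- **The inflated SEs seldom reach the report.** They belong to the starting model. Selection keeps both variables in only about 2% to 4% of datasets when Ht is the driver, so severalfold inflation or reversed signs should not be expected in the selected model.
- **Confirmation does not rest on selection alone.** Section 8.7 says the association of CE with each listed variable will be examined, and 8.1.2 gives Ht its own endpoint. A simple Ht–CE result would be available and well powered at a correlation of 0.3 or more. The AUROC should also change little according to which near-duplicate is kept.

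All four stand, and they narrow the point. They do not remove it. The primary analysis in 8.7.1 is the stepwise model, and 8.7.2 gives the Ht–CE endpoint no method of its own. The descriptive purpose stated in 8.5 does not help either, because the plan still selects on significance and aims to confirm a named association.

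**Conclusion.** The point holds as a risk of mislabelling in the multivariable results. Followed as written, the plan can report Hb where Ht is responsible: in about 18% to 36% of datasets if Ht is the only driver, and about half if the signal is shared.

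That both variables are candidates and Ht is unprotected is certain from the text. The percentages rest on an assumed Ht–Hb correlation (0.90 to 0.98), an assumed Ht–CE correlation (0.24 to 0.4), a 0.05 stay threshold and an assumed covariate structure. A stronger Ht–CE correlation combined with a weaker Ht–Hb correlation reduces the figure, to about 10% at 0.5 and 0.90. The documents do not support a claim that the red-cell effect would be missed, or that the study could not confirm the Ht finding by any route. The plan should be changed, but the problem does not invalidate the study.

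**What to change.** In 8.7, 8.7.1 and 8.7.2:

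- Pre-specify Ht as the single red-cell term in the linear and logistic multivariable models.
- Keep Ht in those models whatever selection does with the other variables, and report its estimate (or odds ratio) with a 95% CI.
- Report Hb descriptively and univariably, or in one sensitivity model where it replaces Ht.

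Removing Hb from the candidates is not enough by itself: at an Ht–CE correlation of 0.3, elimination would still drop Ht in about 13% to 14% of datasets. Hb need not be deleted from the endpoint variables in 8.1.1 and 8.1.2, because univariable reporting covers it.

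The cost is small but not nil. Section 9 requires ethics committee approval of any amendment, and the study would give no estimate of Hb adjusted for Ht. At the assumed correlations that estimate would be very imprecise. No new data are needed.

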8.7.1 Primary Endpoint: analysis

Influence of biological variables on CD34+ CE will be evaluated using a stepwise backward regression analysis; correlation intensity will be assessed using generalized linear model of regression and strength of correlation will be determined by estimate and standard error value.

8.7.2 Secondary Endpoint: Analysis

The association of biological variables with adequate CD34+ CE will be evaluated using linear logistic model of regression and strength of correlation was assessed evaluating Odds Ratio values. Accuracy of clinical prediction model for optimal CD34+ CE will be evaluated by estimating AUROC.

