8.1.2 Secondary Endpoints

- Correlation of clinical (age, sex, type of donor, diagnosis, recent RBC transfusion) and biochemical variables (pre-LP values of Ht, Hb, WBC and PLT) with an adequate ($\geq 60\%$) CD34+ CE.
- Correlation of pre-LP Ht levels and recent (≤ 60 days) RBC transfusion with CD34+ CE, especially in the autologous setting.
- AUROC (Area Under the ROC Curve) of a pre-LP model based on clinical parameters aimed at predicting an adequate ($\geq 60\%$) CD34+ CE.

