8.2.1 Study Population

We will consider consecutive patients and donors referred to the Apheresis Unit within the Transfusional Medicine Department of Fondazione IRCCS Ca' Granda Ospedale Maggiore Policlinico in Milan (from 1/1/2021 to 31/12/2022) for PBSC collection. Total study population: 113 subjects of which 74 hematological/non hematological patients and 39 stem cell donors.

Patients are defined as subjects affected by a hematological or non-hematological disease for which an autologous stem cells transplantation is recommended. These cases are referred as autologous use of stem cells.

Stem cells donors are volunteer healthy subjects who have decided to undergo the procedures needed to collect blood stem cells. These subjects can donate their blood stem cells in favor of a blood relative or, through subscription of a specific registry (IBMDR – International Bone Marrow Donor Registry), to an unknown subject. These cases are referred as allogenic use of stem cells.

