8.3 Variables

Dipartimento Area dei Servizi
SC Medicina Trasfusionale

Direttore: [name]

Tel. Segreteria Direzione: [name]

E-mail: [contact]; [contact]

The following variables will be collected:

- Clinical parameters: age (years), gender (male or female), body weight (kg), type of PBSC use (autologous or allogenic), date of apheresis procedure, type of venous access (peripheral veins or central venous access), total hematic volume (liters), type of mobilization (chemotherapy, G-CSF, Plerixafor), diagnosis (only for autologous setting: multiple myeloma, non-hodgking lymphoma, non haematological disease), RBC transfusion within 60 days before apheresis (yes or not).
- Biochemical parameters: complete blood count pre-LP (cell/mcL), complete blood count on apheresis product (cell/mcL), CD34+ count pre-LP, post-LP and in apheresis product (cell/mcL; cellx106 and cellx106/kg).
- Procedures parameters: total blood volume processed (L), total apheresis product volume (mL)

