8.9 Study Limits

We will try to correct two possible bias within our cohorts:

- by excluding patients affected by Acute Lymphoblastic Leukemia who underwent apheresis procedure in order to collect a salvage CD34+ autologous backup. Those patients are characterized by abnormally high pre-LP CD34+ counts due to disease immunophenotype (often CD34+) and low bone marrow disease burden. Moreover the practice of collecting an autologous CD34+ backup in case of allogeneic engraftment failure or disease relapse, although not detrimental for patients, it's not supported by strong practicing evidence.
- By considering only the first apheresis procedure for each patients in order to avoid any possible selective bias.

The main limits of this study could be:

- the small cohort dimension which do not allow significant evaluations about influence of underlying disease, mobilization regimens and poor mobilizing condition.
- the retrospective nature of data which do not allow to clearly assess influence and utility of RBC transfusion pre-LP.

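### Section 8.7.2 reads strength of association with CE ≥60% from unpenalised logistic odds ratios with 7 to 10 candidate slopes for at most 113 subjects, so these odds ratios are modestly biased away from 1

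*Combined protocol and SAP*

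**What the plan says.** All references are to the combined protocol and SAP.

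- **Model and effect measure (8.7.2).** The association with adequate CE "will be evaluated using linear logistic model of regression and strength of correlation was assessed evaluating Odds Ratio values". No estimator is named. Neither penalisation nor shrinkage is mentioned, and nothing is said about a level whose subjects all fall on one side of 60%.
- **Factors in the endpoint (8.1.2).** "Correlation of clinical (age, sex, type of donor, diagnosis, recent RBC transfusion) and biochemical variables (pre-LP values of Ht, Hb, WBC and PLT", which makes nine factors.
- **Diagnosis (8.3).** It is recorded as "diagnosis (only for autologous setting: multiple myeloma, non-hodgking lymphoma, non haematological disease", so it has three levels, in patients only.
- **Factors in the analysis section (8.7).** "age, sex, type of donor (patients vs healthy donors), hematocrit, hemoglobin level, WBC counts, platelets count", which makes seven. Diagnosis and transfusion are missing, although the same section also requires adjustment for clinical confounders that it does not list.
- **Selection (8.7).** "the selection of variables to be included in multivariable models will be performed by Backward stepwise regression".
- **Size (8.2.1, 8.9).** "Total study population: 113 subjects of which 74 hematological/non hematological patients and 39 stem cell donors". The unit is one procedure per subject: "By considering only the first apheresis procedure for each patients in order to avoid any possible selective bias".
- **Stated limit (8.9).** The protocol concedes that the cohort is too small to assess the effect of underlying disease. It gives no analytic consequence.

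**The concern.** Maximum-likelihood estimates in logistic regression are biased away from the null in small samples. The bias grows as the smaller outcome class shrinks relative to the number of slopes. Here the odds ratio is the stated measure of strength for the first secondary endpoint, and hematocrit, the factor whose relation to CE the protocol most wants to confirm, is among those affected. The reported effects would on average be somewhat too large.

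A second mechanism is conditional. If a small diagnosis level has all its subjects in one CE class, its maximum-likelihood odds ratio has no finite value. Software may still print a very large number, and nothing in 8.7.2 tells the analyst how to treat it.

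**Working it through.** The plan states no power, event count or calculated sample size, so there is no figure to reproduce. The split 74 + 39 = 113 is consistent.

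**1. Candidate slopes.** The 8.7 list has seven single-slope factors: 7. The 8.1.2 list has eight single-slope factors (age, sex, donor type, transfusion, Ht, Hb, WBC, PLT). Three-level diagnosis within patients adds two more once donor type is in the model: 8 + 2 = 10.

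**2. Subjects in the smaller CE class per slope.** Formula: 113 × min(p, 1−p) / k, where p is the share with CE ≥60% (not given in the documents) and k is the number of slopes. One procedure per subject is taken to apply to donors too, so there are at most 113 rows.

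| p | smaller class | k = 7 | k = 10 |
|---|---|---|---|
| 50% | 56.5 | 8.07 | 5.65 |
| 70% | 33.9 | 4.84 | 3.39 |
| 80% | 22.6 | 3.23 | 2.26 |

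The first row is the best possible case.

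**3. Size of the bias.** All simulations used 113 subjects (74/39). Effect sizes, the share with CE ≥60% and the diagnosis counts are assumptions.

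- *Simulation A:* true log odds ratio for Ht 0.60 per 5 points, p = 50-82%, 9 slopes with Hb left out, 3-5 non-haematological patients. The mean maximum-likelihood estimate was 0.67-0.71. Since 0.67/0.60 = 1.12 and 0.71/0.60 = 1.18, it is 12-18% too large. Firth gave 0.59-0.61, with root mean squared error 14-19% lower. With the 8.7 list the bias was 9-13%.
- *Simulation B:* true odds ratio 2 for sex and for Ht per SD, p = 50-85%, Hb included (correlation with Ht about 0.95), 600 datasets per scenario. With 10 slopes, maximum likelihood gave 2.13-2.47 for sex and 2.09-2.74 for Ht, and Firth gave 1.96-2.08 and 1.93-2.10. With 7 slopes, maximum likelihood gave 2.10-2.21 and 2.14-2.55, and Firth 1.97-1.99 and 1.99-2.23. For sex, ln 2.10/ln 2 = 1.07 and ln 2.47/ln 2 = 1.30, so the log odds ratio is 7-30% too large, worst at p = 85%. The Ht figures are noisier because of the overlap with Hb.
- *Simulation C:* true log odds ratio for Ht 0.60, Hb left out. Maximum likelihood gave 0.67-0.71 and Firth 0.58-0.62. Firth's root mean squared error was about 10-20% lower even with the 8.7 list. Maximum-likelihood interval coverage was about 91-96%.

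**4. Divergence, if diagnosis is fitted.** The chance that all n subjects of a level share one outcome is p^n + (1−p)^n, ignoring other covariates:

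| n | p = 50% | p = 70% | p = 80% |
|---|---|---|---|
| 3 | 25% | 37% | 52% |
| 5 | 6% | 17% | 33% |
| 10 | 0.2% | 3% | 11% |
| 15 | <0.1% | 0.5% | 3.5% |

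In simulation B (p = 50-85%) the non-haematological odds ratio diverged in 24-72% of datasets with 3 subjects, 8-52% with 5, 0.2-28% with 10 and 0-15% with 15. With the 8.7 list there was none at p = 50-70%, and large or divergent coefficients appeared in about 6% at p = 85%. Simulation A found separation in 0-3% with that list, and simulation C in under 1%.

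**The case against.** Several stronger readings are tempting, and the documents do not support them.

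- **That odds ratios will become infinite.** A reader might infer this from the three diagnosis levels. No count per diagnosis is given, and Section 8.7 does not list diagnosis as a factor. The risk is large with 3-5 subjects in a level, much smaller with 10-15 unless the outcome is very unbalanced, and close to absent with the 8.7 list unless nearly all subjects reach 60%.
- **That a ten-slope model is pre-specified.** Ten is an upper bound. Section 8.7 selects by backward elimination and promises no full-model odds ratios, though elimination starts from the candidate set, and the unlisted confounders could bring diagnosis in.
- **That the plan ranks factors by odds ratio.** It says only that strength is assessed by odds ratios.
- **That the reported intervals would mislead.** Coverage stayed near 91-96%. A separate simulation without diagnosis (6 slopes, Hb omitted, true log odds ratio 0.60) gave means of 0.65-0.67 with SD 0.24-0.31 and coverage 94-95%. The bias there is about 0.2 SD: (0.65−0.60)/0.24 = 0.21 and (0.67−0.60)/0.31 = 0.23. Adding Hb raised the SD to 0.72-0.96, so Ht/Hb collinearity costs far more precision than this bias costs accuracy.

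It is also fair to say that Section 8.9 already cautions against reading the diagnosis effect, that Section 8.5 calls the analysis descriptive, and that Firth is a partial remedy. For a level of 3-5 subjects with p = 70-85%, its median odds ratio was 1.1-1.6 against a true 2.

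These arguments limit the size of the point. They leave the direction of the bias, which appears with the shorter list too, and the absence of any rule for a one-sided level.

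**Conclusion.** The point holds in a moderate form. With at best 8.1 (7 slopes) or 5.7 (10 slopes) subjects of the smaller CE class per candidate slope, unpenalised odds ratios for CE ≥60% are modestly exaggerated. The log odds ratio for hematocrit is roughly 10-18% too large under the assumed inputs, and more if the outcome is very unbalanced. Confidence interval coverage stays close to nominal, so the main effect is on point estimates, which is what 8.7.2 reads as strength.

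Divergence of a diagnosis odds ratio is a possibility only, conditional on diagnosis being fitted and on a level being very small. The conclusion assumes a maximum-likelihood fit, which is the ordinary meaning of an unqualified logistic model, and it rests on assumed effect sizes and an assumed share with CE ≥60%.

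**What to change.** In Section 8.7.2, state that:

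1. The models for CE ≥60% are fitted by Firth-penalised logistic regression, and the odds ratios are reported with profile penalised-likelihood 95% confidence intervals.
2. The numbers with CE ≥60% and below are tabulated for each level of each categorical factor. A level with all subjects in one class is reported as counts, and its odds ratio is not interpreted.

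In Sections 8.1.2 and 8.7, use the same factor list, so that it is clear whether diagnosis and recent transfusion enter these models.

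**Cost.** A few sentences and a different fitting option, with no new data. The team should confirm that the planned software offers the method with profile intervals. Odds ratios will be slightly smaller. The intercept needs its usual correction if predicted probabilities are reported; the AUROC is unaffected by that correction because it depends only on ordering. Estimates for tiny levels remain imprecise. Firth does not cure the exaggeration from backward selection: after selection it removed typically only 0.02-0.04 on the log scale.

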7.2 Secondary objectives

- Identify clinical and/or biochemical factors associated with an optimal ($\geq 60\%$) CD34+ CE
- Confirm data, from the published literature, regarding the correlation between Ht and CD34+ CE in a cohort of subjects largely composed by hematological patients.
- Develop a prediction model for optimal ($\geq 60\%$) CD34+ CE using pre-LP clinical and/or biochemical factors.

8. Methods

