8.1 Study Design

This is an observational, retrospective, non-pharmacological, single-center, no profit study conducted on cohort of patients and stem cell donors referred to the Transfusional Medicine Department of IRCCS Ca' Granda Ospedale Maggiore Policlinico in Milan for PBSC harvesting.

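### The AUROC of the CE ≥60% prediction model would be estimated on the subjects used to select and fit it, with no internal validation, so it will be optimistic on average

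*Combined protocol and SAP*

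**What the plan says.** - **Objective (7.2):** "Develop a prediction model for optimal" CE, meaning at least 60%, from factors known before leukapheresis.
- **Endpoint (8.1.2):** "AUROC (Area Under the ROC Curve) of a pre-LP model based on clinical parameters". This is the third of three secondary endpoints and the only performance measure named for the model.
- **Accuracy analysis (8.7.2):** "Accuracy of clinical prediction model for optimal CD34+ CE will be evaluated by estimating AUROC". Nothing further is said on method.
- **Model building (8.7):** "In order to avoid overfitting, the selection of variables to be included in multivariable models will be performed by Backward stepwise regression". No removal threshold is given; the only alpha stated is 0.05, two-sided.
- **Data (8.5, 8.1, 8.9):** "Total study population: 113 subjects of which 74 hematological/non hematological patients and 39 stem cell donors"; "This is an observational, retrospective, non-pharmacological, single-center, no profit study"; and one record per subject, "By considering only the first apheresis procedure for each patients in order to avoid any possible selective bias".
- **Sample-size basis (8.5):** "Due to descriptive nature of the analysis planned, no pre-analysis sample size was determined".
- **Other analyses:** section 8.7.4 (supplemental analysis) is marked not applicable. The limits in 8.9 mention the small cohort but not optimism in the model's accuracy.

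**The concern.** A prediction model is meant for the next donor or patient. An AUROC computed on the data that chose the variables and estimated the coefficients (the apparent AUROC) describes how well the model separates those subjects, and on average it overstates performance in new ones. The plan recognises the risk of overfitting, but the safeguard it names does not address the reported figure. Choosing variables on the same data is itself a source of optimism, and the apparent AUROC takes no account of that step. No interval or calibration measure is planned that might warn a reader. At stake is the answer to the third secondary objective: a weak model could be reported as moderately accurate.

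**Working it through.** The plan states no expected AUROC, so there is no figure of its own to reproduce. The check has four steps.

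**1. Is the same data used throughout?** The documents do not say so outright. It follows from one single-centre cohort, one procedure per subject, and no mention of a split, resampling or outside data. The figure of 113 is an upper limit, because subjects with missing CD34+ counts would drop out.

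**2. How much information is there per parameter?** Section 8.7 lists 7 candidates: age, sex, type of donor, Ht, Hb, WBC and platelets. Sections 8.1.1 and 8.1.2 add diagnosis and recent RBC transfusion. Diagnosis has three categories in 8.3, for the autologous setting only, so it adds two parameters beyond type of donor: 7 + 2 + 1 = 10. The share π reaching CE ≥60% is not stated and is assumed. The smaller outcome class has 113 × min(π, 1 − π) subjects.

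| π | Smaller class | Per parameter, 7 candidates | Per parameter, 10 candidates |
|---|---|---|---|
| 0.5 | 56.5 | 8.1 | 5.7 |
| 0.7 | 33.9 | 4.8 | 3.4 |
| 0.8 | 22.6 | 3.2 | 2.3 |

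**3. How large is the optimism?** The planned procedure was simulated with n = 113, 39/113 donors, a logistic model and backward elimination at p < 0.05. The AUROC on the same data (apparent) was compared with that of the same fitted model in 8,000 new subjects (actual), with 400 runs per scenario. Assumptions: only Ht is truly predictive, and the Ht–Hb correlation is at least 0.95. Optimism = mean(apparent − actual).

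| Candidates | π | No signal | True AUROC about 0.66 | True AUROC about 0.77 |
|---|---|---|---|---|
| 7 | 0.5 | 0.039 | 0.048 | 0.030 |
| 7 | 0.7 | 0.044 | 0.039 | 0.020 |
| 7 | 0.8 | 0.043 | 0.049 | 0.022 |
| 10 | 0.5 | 0.050 | 0.043 | 0.021 |
| 10 | 0.7 | 0.053 | 0.053 | 0.026 |
| 10 | 0.8 | 0.062 | 0.064 | 0.030 |

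- With no signal, 61% to 73% of runs kept no variable. In the runs that did keep a model, optimism averaged 0.13 to 0.16.
- With a true signal, the apparent AUROC exceeded the actual one in about 60% to 78% of runs.
- Further runs varied the removal threshold. With an assumed Ht–CE correlation of 0.4 to 0.5, mean optimism was about 0.03 to 0.05 at p = 0.05 and 0.03 to 0.08 at p = 0.10. With no or weak signal (new-data AUROC at most 0.55 to 0.58) it was 0.04 to 0.11 over the two thresholds.

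**4. Does the correction work?** The bootstrap correction is: corrected AUROC = apparent AUROC − mean over resamples of (AUROC in the resample − AUROC of that resample's model in the original data), with backward selection repeated each time. It was tried with π = 0.5, true AUROC about 0.65, 60 resamples and 120 runs.

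| Candidates | Apparent | Corrected | Actual |
|---|---|---|---|
| 7 | 0.657 | 0.606 | 0.608 |
| 10 | 0.657 | 0.592 | 0.615 |

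The upward bias is removed. With 10 candidates the correction overshoots by 0.615 − 0.592 = 0.023.

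A random split is a poor alternative. By the Hanley–McNeil formula the standard error of an AUROC of 0.65 to 0.75 is already about 0.046 to 0.060 on all 113 subjects, with 30% to 80% reaching CE ≥60%.

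**The case against.** The strongest reply has four parts.

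- **Scope.** The AUROC is one of three secondary endpoints in a retrospective study whose planned analysis section 8.5 calls descriptive. The documents attach no success threshold and no clinical or donor-selection decision to it. This stands, and it limits the severity. It does not remove the bias: the descriptive label explains the missing sample-size calculation, but 7.2 still states a prediction aim.
- **Size.** The background section cites a study of 147 procedures with a moderate positive correlation between Ht and CE, so a no-signal scenario should not be the headline. This also stands. Optimism near 0.11 arose only with removal at p = 0.10, 10 candidates and 80% reaching CE ≥60%, and the plan's only stated alpha is 0.05.
- **Noise.** Much of the bias is no larger than the AUROC's standard error. That is true, but sampling error goes in both directions, whereas this bias is upward on average.
- **Certainty.** A reader might infer that the reported AUROC is bound to be too high, or that the plan openly prescribes estimation on the fitting data. The documents support neither. The bias is an average, and with a true signal the apparent value did not exceed the actual one in roughly a quarter to two-fifths of the main runs. Use of the same data is an inference from silence, though no other data source is described.

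**Conclusion.** The gap is real. As written, the plan yields an apparent AUROC that is optimistic on average, and backward selection does not correct it. Under assumed rates of CE ≥60% of 50% to 80% and 7 to 10 candidate parameters, mean optimism is about 0.02 to 0.06 with removal at p = 0.05 if Ht carries a moderate signal, and up to about 0.08 at p = 0.10. With little or no signal it is about 0.04 to 0.11. These figures also rest on assumed covariate distributions.

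A reader might go further and conclude that the study's main result is compromised. It is not: the primary endpoint (8.1.1, 8.7.1) and the other two secondary endpoints do not use the AUROC. This is a should-fix point on one secondary endpoint.

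**What to change.** Replace the accuracy sentence in 8.7.2 with wording such as:

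> The AUROC will be corrected for optimism by bootstrap, using at least 500 resamples and repeating every model-building step, including backward selection, in each. The optimism-corrected AUROC is the reported measure of accuracy. The apparent AUROC is shown for reference only and labelled as such.

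To make those steps repeatable, section 8.7 should also fix the candidate list for this model and the removal threshold, and should no longer present backward selection as the protection against overfitting. A calibration slope and a confidence interval are optional additions; if an interval is given, its method should be named.

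The cost is a few sentences and a short script, with no new data. The downsides are a lower reported AUROC and possible slight over-correction.
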